1.2.3 Clinical Study Experience

The clinical benefits achieved with the use of use of Pipeline™ Embolization Device have been consistently demonstrated in multiple clinical trials.²⁶⁻³⁶ Pipeline™ Embolization Device demonstrates high efficacy and a good safety profile in treating aneurysms of diverse morphology, ranging from small to more complex and difficult to treat aneurysms (e.g. large aneurysms, wide-

neck aneurysms, or aneurysms with complex morphology).^{27,30,37,39-41} Clinical outcomes from 5 key studies sponsored by Medtronic/Covidien have been summarized below:

Pipeline for Intracranial treatment of Aneurysms (PITA)

The PITA study was the first prospective multicenter trial of a flow-diverting construct for the treatment of complex large and giant IAs.²⁷ Thirty-one subjects with wide-necked (>4 mm) and unfavorable dome/neck ratios (<1.5 mm) and subjects with an IA that had failed previous endovascular treatment were included. Of the 31 aneurysms, 65% were small (<10 mm) and the remaining 35% were large and giant in size. In total, 46 of 47 Pipeline™ device braids were placed successfully (97.9%). In 30 out of 31 subjects, the entire neck of the targeted intracranial aneurysm was covered by the Pipeline™ device braid. Complete aneurysm occlusion was observed in 93.3% (28/30) subjects at 180 days. Two subjects experienced a major periprocedural stroke and no deaths occurred.

Pipeline™ Embolization Device for Uncoilable or Failed Aneurysms (PUFs)

The PUFs study was a multicenter, prospective, single-arm trial to evaluate the safety and effectiveness of the PED in complex large and giant IAs.²⁸ One hundred seven subjects with large and giant unruptured wide-necked aneurysms in the petrous to the superior hypophyseal segment of the ICA were treated with the PED. The aneurysms measured ≥ 10 mm in diameter and had either a neck ≥ 4 mm or no discernable neck. A total of 104 subjects with 106 aneurysms were included in the primary effectiveness cohort. Of the 106 aneurysms, 78 demonstrated complete occlusion without major stenosis at 180 days (73.6%; 95% posterior probability interval: 64.4%–81.0%). At one year, 86.8% (79/91) of the target aneurysms were completely occluded. This rate increased to 95.2% (59/62) complete occlusion at five years. There were no cases of aneurysm recurrence. The primary safety endpoint was the occurrence of major ipsilateral stroke or neurologic death at 180 days, which occurred in six of the 107 subjects (5.6%; 95% posterior probability interval: 2.6%–11.7%). At five year follow-up, the rate of major ipsilateral stroke or neurologic death remained 5.6%.

International Retrospective Study of the Pipeline Embolization Device (IntrePED)

The IntrePED study was a retrospective global post market study of subjects treated with the PED at 17 centers worldwide.²⁹ A total of 793 subjects with 906 aneurysms of various sizes and locations were included. The median follow-up period was 19.3 months with 89% subjects with greater than 1 year follow-up. The overall neurological morbidity rate was 7.4% (59/793) and the neurological mortality rate was 3.8% (30/793). The combined neurological morbidity and mortality rate was 8.4% (67/793). The combined neurological morbidity and mortality for treated ruptured aneurysms was higher at 18.4% (14/76). Data from the IntrePED study report the safety of the PED in the treatment of various IAs in a real-world clinical setting.

Aneurysm Study of Pipeline in an Observational Registry (ASPIRe)

ASPIRe was a prospective, multi-center, single arm, post-market registry of 191 IA patients with 207 aneurysms from 28 worldwide centers who underwent PED treatment. The 207 aneurysms in the study had a median follow-up duration of 6.6 months. The majority of aneurysms treated were saccular and overall average size of treated aneurysms was 14.5mm.

Neurological morbidity was 6.8% (13/191) and the neurologic mortality rate was 1.6% (3/191). The combined rate of neurological morbidity and mortality was 6.8% (13/191), with the most common major adverse event of interest being intracerebral hemorrhage (3.7%, 7/191) followed by ischemic stroke (1.6%, 3/191). Most of the major adverse events (6.3%, 12/191) occurred in the early post-operative phase within the first 30 days following PED treatment.

Aneurysm occlusion was assessed according to the Scale of Roy at last visit for all subjects with imaging follow-up of at least 6 months. The median follow-up duration was 7.8 months and complete occlusion was reported in 75% of subjects (77/103). The use of embolic coils was the most common adjunctive therapy and was employed in 17.3% (33/191) of subjects.

The ASPIRe registry, as a comprehensive evaluation of PED use in the real world, confirmed that the PED is safe when used for the treatment of IAs in routine clinical practice, reporting a 6.8% rate of associated major morbidity and neurological mortality.

1.3 Rationale of the Clinical Study

The Pipeline™ Embolization Device demonstrates high efficacy and a good safety profile in treating aneurysms of diverse morphology. Continued development of the PED delivery system resulted in the Pipeline™ Flex Embolization Device (PFED), which incorporates a resheathing mechanism, allowing the physicians to reposition and redeploy the PED braid. Additionally, polytetrafluoroethylene (PTFE) sleeves are used in place of the protective coil, resulting in the elimination of the need to torque the delivery system to release the PED braid. The latest developmental modification to the PED system is Shield Technology™. Shield Technology™ utilizes a phosphorylcholine (PC) surface treatment to the existing implant combined with the PFED delivery system. The Shield Technology™ surface treatment applied to the implant is an inert, PC polymer material that is chemically bonded to the braid surface. The polymer is a chemically derived material, created to mimic the outer membrane of a human red blood cell. Shield Technology™ reduces the material thrombogenicity of the braid surface compared to the current bare metal PFED implant based on bench data with human platelets and plasma. The study described herein will evaluate the performance of the Pipeline™ Flex Embolization Device with Shield Technology™ in a broad real-world clinical setting.

Platelet inhibition with dual antiplatelet therapy (DAPT); consisting of aspirin and a thienopyridine, is necessary for the prevention of acute or subacute thrombosis and related complications after neurointerventional procedures.⁴² DAPT has been associated with a reduction in thromboembolic events, but has also been implicated as a potential factor contributing to the rates of ischemic and hemorrhagic complications associated with PED placement.⁴² Current DAPT protocols used in PED patients are developed based on studies in the field of cardiology and interventional radiology. In addition, there is no consensus on the optimal DAPT regimen, dose, and duration.⁴³ This study aims to collect data on platelet function testing, DAPT regimens, optimal dose, and post-PED DAPT duration to identify their association with thrombotic and hemorrhagic adverse events in the clinical setting and evaluate related clinical outcomes.

2 DEVICE DESCRIPTION

2.1 Intended Use of Device

The latest developmental modification to the Pipeline™ Flex Embolization Device (PFED) system is Shield Technology™. Shield Technology™ utilizes a phosphorylcholine (PC) surface treatment to the implant combined with the PFED delivery system. The Shield Technology™ surface treatment applied to the implant is an inert, PC polymer material that is chemically bonded to the braid surface. The polymer is a chemically derived material, created to mimic the outer membrane of a human red blood cell. Shield Technology™ reduces the material thrombogenicity of the braid surface compared to the bare metal PFED implant based on bench data with human platelets and plasma.

[figure not shown]
The Pipeline™ Flex Embolization Device with Shield Technology™ is intended for endovascular embolization of cerebral aneurysms and is designed to be placed across the opening (or 'neck') of a brain aneurysm and redirect blood flow away from the aneurysm, causing the blood within the aneurysm to clot. The device is designed for use in the neurovasculature.

2.1.1 Device Name

Name: Pipeline™ Flex Embolization Device with Shield Technology™.

A photo and diagram of the Pipeline™ Flex Embolization Device with Shield Technology™ is shown in Error! Reference source not found. **Figure 2.1.**

Figure 2-1. Pipeline™ Flex Embolization Device with Shield Technology™

Left, photo of the braid. Right, diagram of the distal end of the Pipeline™ Flex Embolization Device with Shield Technology™ delivery system loaded into the introducer sheath.

All the Pipeline™ Flex Embolization Device with Shield Technology™ models used in this trial are commercially available, CE-Marked and used within intended use in all the involved countries, including Australia. The table below reports all the available models' numbers:

MODEL NUMBER	Vessel (mm)	Length (mm)
PED2-250-10	2,50	10
PED2-250-12	2,50	12
PED2-250-14	2,50	14
PED2-250-16	2,50	16
PED2-250-18	2,50	18
PED2-250-20	2,50	20
PED2-275-10	2,75	10
PED2-275-12	2,75	12
PED2-275-14	2,75	14
PED2-275-16	2,75	16
PED2-275-18	2,75	18
PED2-275-20	2,75	20
PED2-300-10	3,00	10
PED2-300-12	3,00	12
PED2-300-14	3,00	14
PED2-300-16	3,00	16
PED2-300-18	3,00	18
PED2-300-20	3,00	20
PED2-300-25	3,00	25
PED2-300-30	3,00	30
PED2-300-35	3,00	35
PED2-325-10	3,25	10
PED2-325-12	3,25	12
PED2-325-14	3,25	14
PED2-325-16	3,25	16
PED2-325-18	3,25	18
PED2-325-20	3,25	20
PED2-325-25	3,25	25
PED2-325-30	3,25	30
PED2-325-35	3,25	35
PED2-350-10	3,50	10
PED2-350-12	3,50	12
PED2-350-14	3,50	14
PED2-350-16	3,50	16
PED2-350-18	3,50	18
PED2-350-20	3,50	20
PED2-350-25	3,50	25
PED2-350-30	3,50	30
PED2-350-35	3,50	35
PED2-375-10	3,75	10

PED2-375-12	3,75	12
PED2-375-14	3,75	14
PED2-375-16	3,75	16
PED2-375-18	3,75	18
PED2-375-20	3,75	20
PED2-375-25	3,75	25
PED2-375-30	3,75	30
PED2-375-35	3,75	35
PED2-400-10	4,00	10
PED2-400-12	4,00	12
PED2-400-14	4,00	14
PED2-400-16	4,00	16
PED2-400-18	4,00	18
PED2-400-20	4,00	20
PED2-400-25	4,00	25
PED2-400-30	4,00	30
PED2-400-35	4,00	35
PED2-425-10	4,25	10
PED2-425-12	4,25	12
PED2-425-14	4,25	14
PED2-425-16	4,25	16
PED2-425-18	4,25	18
PED2-425-20	4,25	20
PED2-425-25	4,25	25
PED2-425-30	4,25	30
PED2-425-35	4,25	35
PED2-450-10	4,50	10
PED2-450-12	4,50	12
PED2-450-14	4,50	14
PED2-450-16	4,50	16
PED2-450-18	4,50	18
PED2-450-20	4,50	20
PED2-450-25	4,50	25
PED2-450-30	4,50	30
PED2-450-35	4,50	35
PED2-475-10	4,75	10
PED2-475-12	4,75	12
PED2-475-14	4,75	14
PED2-475-16	4,75	16
PED2-475-18	4,75	18
PED2-475-20	4,75	20
PED2-475-25	4,75	25
PED2-475-30	4,75	30

PED2-475-35	4,75	35
PED2-500-10	5,00	10
PED2-500-12	5,00	12
PED2-500-14	5,00	14
PED2-500-16	5,00	16
PED2-500-18	5,00	18
PED2-500-20	5,00	20
PED2-500-25	5,00	25
PED2-500-30	5,00	30
PED2-500-35	5,00	35

2.2 Indication for Use

The Pipeline™ Flex embolization device with Shield Technology™ is intended for endovascular embolization of cerebral aneurysms.

2.3 Contraindications

- Patients who have not received antiplatelet agents prior to the procedure.
- Patients with active bacterial infection.
- Patients in whom antiplatelet and/or anticoagulation therapy is contraindicated.
- The Pipeline™ Flex embolization device with Shield Technology™ should not be used alone as sole therapy for acutely ruptured aneurysms.

2.4 Device Labeling

The Pipeline™ Flex Embolization Device with Shield Technology™ is approved for commercialization in the countries that will be participating in this study and will be used within its intended use as specified in the approved labeling. The Pipeline™ Flex Embolization Device with Shield Technology™ will be labeled as commercially available and in accordance with applicable language requirements.

2.5 Device Tracking

The Pipeline™ Flex Embolization Device with Shield Technology™ is traced by lot number. The lot number of each Pipeline™ Flex Embolization Device with Shield Technology™ used in this study will be captured on the case report forms. Due to commercial availability, shipments will not be tracked for the study.

2.6 Pre-Clinical Testing

Biocompatibility Summary

All biocompatibility tests for The Pipeline™ Flex Embolization Device with Shield Technology™ were completed, and all test results passed the acceptance criteria (per ISO 10993-1:2009 and FDA G95-1).

Study Summary

[Redacted text block]

Overall Study Conclusion

[Redacted text block]

Study Summary

[Redacted text block]

Taken together, the results show that the Pipeline™ Flex Embolization Device with Shield Technology™ is safe and efficacious in this animal model.

3 STUDY OBJECTIVE

The study objective is to assess the performance of the Pipeline™ Flex Embolization Device with Shield Technology™ in a large real-world, post-market setting.

3.1 Data Analyses

The following data will be analyzed in this study:

- Antiplatelet therapy regimen
- Adverse events related to antiplatelet therapy
- Platelet reactivity testing results
- Moderate and Severe bleeding events utilizing GUSTO criteria
- All intracranial hemorrhages and delayed intracranial hemorrhages (>30 days post-procedure)

- Index procedure time
- Number of Pipeline™ Flex Embolization Device with Shield Technology™ utilized
- Device deployment success rate at target site
- Aneurysm occlusion at 6 months, 1 year and at last follow-up
- Recurrence and retreatment rates at 1 year post-procedure and at last follow-up
- The composite percentage of patients with modified Rankin Scale of 0-2 or no change from baseline at 1 year and at last follow-up.
- Occurrence of major stroke in the territory supplied by the treated artery or neurological death. Stroke events will be further characterized based on whether:
 - Event was caused by thromboembolic events
 - Event was caused by side-branch occlusion due to the study device

For the purposes of this study protocol, stroke is defined as a focal neurological deficit of presumed vascular origin persisting more than 24 hours from symptom onset and a neuro-imaging study or other quantitative study that does not indicate a different etiology. The 24-hour criterion is excluded if the subject undergoes cerebrovascular surgery or dies during the first 24 hours of symptom onset.

The definition includes:

- Subjects presenting with clinical signs and symptoms suggestive of subarachnoid hemorrhage, intracerebral hemorrhage, or cerebral infarction.
- Sudden loss or worsening of visual acuity due to retinal artery occlusion or retinal emboli.

The definition excludes:

- Slowly progressive cranial nerve palsies or progressive visual field deficits due to continued aneurysm growth.
- Stroke events in cases of blood disorders such as leukemia or external events such as trauma.

Stroke severity will be graded by the investigator as major or minor:

- Major Stroke: A stroke, which is present after seven days and increases the NIH Stroke Scale of the subject by ≥ 4 .
- Minor Stroke: A stroke, which resolves completely within seven days OR increases the NIH Stroke Scale of the subject by ≤ 3 .

Neurological death is any subject death due to an underlying neurologic cause.

The safety events noted for analysis will be adjudicated by an independent clinical events committee (CEC) (**Section 8.1**). Aneurysm occlusion and recurrence will be evaluated by an independent core laboratory (**Section 8.2**).

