4.2 Number of Sites and Subjects

Up to 200 subjects at up to 25 sites worldwide may participate. Each participating investigational site should attempt to enroll at least 1 subject and will be allowed to enroll up to 30 subjects who meet all study eligibility criteria.

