4.3 Study Population

The study population will consist of subjects who have an intracranial aneurysm and are enrolled in the study. The treated aneurysm may be ruptured (with a Hunt and Hess grade of ≤ 3) provided that the Pipeline™ Flex Embolization Device with Shield Technology™ is used according to its Instructions for Use and its intended use during the treatment regimen.

For subjects with more than one aneurysm requiring treatment, the following guidance is to be followed for subjects to be enrolled in the study.

- If more than one aneurysm can be covered by a single Pipeline device or two overlapped devices, the multiple aneurysms treated by that device(s) may all be included in the study. A maximum of two overlapped devices in consecutive arterial segments will be permitted. The largest aneurysm meeting criteria will be designated the target aneurysm. For equal sized aneurysms, the Core Lab will designate the target aneurysm.
- If the subject has more than one aneurysm and all aneurysms requiring treatment cannot be covered by a single Pipeline device or two overlapped devices, the non-target aneurysms should be treated first. After waiting at least 30 days per exclusion criterion #1 below, the subject may return for Pipeline treatment of the target aneurysm.

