7.2.2 General Conventions for Summarization

Summary statistics will consist of the number and percentage of responses or counts at each level for categorical variables (e.g. gender). For continuous variables, the sample size (n), mean, median, standard deviation (SD), minimum, and maximum values will be presented.

All mean and median values will be formatted to one more decimal place than the measured value. Standard deviation values will be formatted to two more decimal places than the measured value. Minimum and maximum values will be presented with the same number of decimal places as the measured value.

The number and percentage of responses will be presented in the form XX (XX.X%).

- All summary tables will include the analysis population sample size (i.e., number of subjects).
- Relative Study Day 0 is defined as the day the patient underwent the study procedure. All study days are determined relative to the day the patient underwent the study procedure.
- Baseline values will be defined as those values recorded immediately prior to the study procedure.
- Change from baseline for differences will be calculated as follows:

$$\text{Change} = \text{Post-baseline value} - \text{baseline value}$$

- Missing data may have an impact upon the interpretation of the trial data. The primary presentation of the overall primary endpoint results will be based on the observed data with multiple imputation for missing data using SAS PROC MI. A methodology is also defined in this section for addressing missing dates.
- Date variables will be formatted as DDMMYYYY for presentation; SAS Date9. format.

Data from this study, when applicable will be presented in a listing format. All listings will be sorted by patient number and date, as applicable.

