Subjects may undergo (as indicated by site per standard of care) a neurologic examination and assessment using the mRS and NIHSS at baseline and also prior to the procedure. Data will be summarized and reported in a table entitled Summary of Neurological Assessments at Baseline (ITT population); a similar table will be restricted to the ICA population. The summary will include the baseline results for the mRS (Baseline) and NIHSS (recorded pre-procedure). The mRS, results will be presented using counts and percentages for each mRS score. For the NIHSS, results will be summarized using descriptive statistics as observed.

A NIHSS table will be presented in a listing format entitled NIH Stroke Scale (NIHSS) Scores will contain the baseline pre-procedure and post-procedure scores by patient, as well as the date and time the score was recorded. This listing will be sorted by patient number. As the screening/baseline assessments may be performed prior to the procedure at Day 0 some subjects will have only a single value for NIHSS. In this case the screening/baseline value will be left blank in the listing. A listing entitled Modified Rankin Scale (mRS) Scores will contain the pre-procedure and post-procedure scores by patient and date the score was recorded. This listing will be sorted by patient number.

Platelet Reactivity Test Results

Data will be summarized and reported in a table entitled Summary of the Platelet Reactivity Test Results Recorded at Baseline (ITT population); a similar table will be restricted to the ICA population. The last results prior to the procedure will be reported for each patient. The platelet test results will be summarized using descriptive statistics: n, arithmetic mean, standard deviation, median, range (i.e., minimum and maximum values). Subjects with missing data that cannot be resolved prior to database lock will not be included in the tabulation and excluded from the summary statistics; all data will be presented in a listing. A summary of the platelet reactivity data recorded after the procedure will be presented in a table entitled Summary of Post-Procedure Platelet Reactivity Test Data; a similar table will be restricted to the ICA population. The supportive data for Table platelet reactivity will be presented in a listing format entitled Platelet Reactivity Test Results. This listing will be sorted by patient number. The individual elements to be presented from the CRF are presented below.

[Redacted content]

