- Number of times re-sheathing was attempted. The count (0, 1, 2, or >2) comes directly from the clinical case report form.
- Entire IA neck covered by the study device. Complete neck coverage has a binary outcome and comes directly from the core lab
- Side branches covered by the study device. Complete side branch coverage has a binary outcome and comes directly from the core lab
- Post-deployment stasis (complete, significant, or no disruption of inflow jet); evaluated as 1 of 3 possible states, comes directly from the core lab
- Target aneurysm partially thrombosed; a binary endpoint that comes directly from the core lab
- Percentage of target aneurysm thrombosis; a continuous endpoint that comes directly from the core lab
- Achievement of wall apposition; a binary endpoint that comes directly from the core lab.

The duration of the procedure (min) will also be summarized and presented using descriptive statistics.

The supportive data for these series of tables will be presented in a listing entitled *Device and Peri-Procedure Analyses*. This listing will be sorted by patient number.

Overall Summary of the Post-Procedure Variables Recorded Over Time

The post-procedure analyses will be summarized for the following 5 time points: Post-Procedure Discharge, 1 Month Post-Procedure, 3 Months Post-Procedure, 6 Months Post-Procedure, and 1 Year Post-Procedure. The following 10 separate parameters will be summarized:

- Aneurysm occlusion (Class 1: Complete obliteration, Class 2: Residual neck, or Class 3: Residual Aneurysm), derived from the post-procedure imaging adjudicated by core lab.
- Modified Rankin Scale (mRS). The mRS score at 1 year will be dichotomized (>2 vs. ≤ 2) and summarized using counts, percentages, and 2-sided 95% exact binomial confidence intervals.
- NIH Stroke Scale (NIHSS)
- Platelet reactivity testing
- Change in antiplatelet therapy because of the platelet reactivity testing
- Retreatment of the target aneurysm
- Major stroke in the territory supplied by the treated artery or neurological death at 30 days post-procedure due to procedural complications
- Intracerebral hemorrhage (ICH) > 30 days post-procedure (Delayed ICH)
- Parent artery stenosis (per Core Lab)
- Device migration (per Core Lab)

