7.12 Changes to Planned Analysis

Planned analyses will be performed as indicated and per CIP. Other analyses can be conducted addition to the prespecified analyses as to further elucidate findings that may be useful to the Sponsor or the medical community.

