7.13.3 Post-Procedure Analyses

The first series of **Post-Procedure** analyses to be summarized will address the outcomes after the procedure. Within this series, there are 9 separate parameters:

- Aneurysm occlusion (Class 1: Complete obliteration, Class 2: Residual neck, or Class 3: Residual Aneurysm), derived from the post-procedure imaging adjudicated by Core Lab.
- Modified Rankin Scale (mRS); a multinomial endpoint that comes directly from the site reported case report form for evaluating the intra-patient over time and the change from baseline. The mRS will be scored for each patient by an evaluator at the clinical site. The mRS is a well-accepted and defined scoring system for measuring the degree of disability or dependence in the daily activities of people who have suffered a stroke using a multinomial ordinal scale:
 - 0 No symptoms at all
 - 1 No significant disability despite symptoms; able to carry out all usual duties and activities
 - 2 Slight disability; unable to carry out all previous activities, but able to look after own affairs without assistance

The mRS score at 1 year will be dichotomized (>2 vs. ≤ 2) and summarized using counts, percentages, and 2-sided 95% exact binomial confidence intervals.

- NIH Stroke Scale (NIHSS); a continuous endpoint that comes directly from the site reported clinical case report form for evaluating the intra-patient over time and the change from baseline. The NIHSS is a 15-item neurologic examination stroke scale used to evaluate the effect of acute cerebral infarction on the levels of consciousness, language, neglect, visual-field loss, extraocular movement, motor strength, ataxia, dysarthria, and sensory loss.
- Platelet reactivity testing, based on the VerifyNow, VASP, MEA, TEG, LTA testing reported as a percentage. A continuous endpoint that comes directly from the site reported clinical case report form.
- Change in antiplatelet therapy because of the platelet reactivity testing; a binary variable and comes directly from the site reported clinical case report form.
- Retreatment of the target aneurysm; a binary variable adjudicated by the imaging core laboratory. The recurrence of the aneurysm will be summarized using the percentage of subjects that experience aneurysm recurrence. Aneurysm recurrence is defined as an aneurysm that achieves complete occlusion at 6 months post-procedure, and then is no

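### The protocol's mRS good-outcome rule scores some improvers as failures, and the SAP's visible mRS summary uses a different rule that ignores baseline

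*Protocol*

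**What the plan says.** **Protocol.** Section 3.1, repeated in 9.4, lists as a planned result "The composite percentage of patients with modified Rankin Scale of 0-2 or no change from baseline at 1 year and at last follow-up". Neither section says whether an improvement counts as no change.

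**SAP, meaning of change.** Section 7.2.2 fixes the arithmetic: "Change from baseline for differences will be calculated as follows", followed by post-baseline value minus baseline value. On that definition no change means a difference of zero.

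**SAP, mRS summary.** Sections 7.7 and 7.13.3 both state: "The mRS score at 1 year will be dichotomized". The split is above 2 against 2 or below, with counts, percentages and exact 95% limits. Baseline does not enter the split, and last follow-up is not mentioned. Section 7.13.3 also describes mRS as "a multinomial endpoint that comes directly from the site reported case report form for evaluating the intra-patient over time and the change from baseline", but gives no rule for classing a subject as better, unchanged or worse.

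**SAP, link to the protocol.** Section 7.12 says: "Planned analyses will be performed as indicated and per CIP".

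**Who can be enrolled.** Protocol 4.3 admits ruptured aneurysms up to Hunt and Hess grade 3, and no criterion in 4.3.1 or 4.3.2 sets a limit on baseline mRS. Baseline mRS itself depends on site practice: "Subjects may undergo (as indicated by site per standard of care) a neurologic examination and assessment using the mRS and NIHSS at baseline" (SAP 7.6). The SAP schedule marks it optional at baseline and at each follow-up visit, and required at the procedure.

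**The concern.** A good-outcome rule should never rank a subject who got better below one who stayed the same. The protocol rule does so for some subjects with moderately severe or severe disability at entry. The SAP split does not misorder outcomes, but it counts disability present before treatment as a poor result of treatment.

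The two documents also define the 1-year mRS result differently. Two programmers, each following one document, could report different good-outcome rates from the same data. There is no control arm in which the same misclassification would occur. SAP section 3 intends to contrast the results with earlier Pipeline studies and to inform a US indication evaluation. Of the visible mRS summaries, only the split at 2 is assigned a confidence interval.

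**Working it through.** The documents give no expected rate, sample size or threshold for mRS, so there is no figure of theirs to reproduce. The check has two parts.

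**1. Every possible transition.** Baseline mRS 0–5 by follow-up mRS 0–6 gives 6 × 7 = 42 cells: 15 improvements, 6 unchanged and 21 worsenings. Let b be baseline and f follow-up. A subject fails when:

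- Protocol rule, literal: f ≥ 3 and f ≠ b
- SAP split: f ≥ 3
- Proposed rule (0–2 or no worse than baseline): f ≥ 3 and f > b

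| Cells counted as failure | Protocol | SAP | Proposed |
|---|---|---|---|
| Improved (15) | 3 | 3 | 0 |
| Unchanged (6) | 0 | 3 | 0 |
| Worsened (21) | 18 | 18 | 18 |

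The three failing improvements are 4 to 3, 5 to 3 and 5 to 4, under both existing rules. The other 12 improvements end at 0–2 and count as success. The three failing unchanged cells under the SAP are 3 to 3, 4 to 4 and 5 to 5. The three worsenings that every rule misses, including the proposed one, are 0 to 1, 0 to 2 and 1 to 2.

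**2. Possible size.** The maximum N is 200 (Protocol 4.2: "Up to 200 subjects at up to 25 sites worldwide may participate"). Everything else here is an assumption:

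- q, the share with baseline mRS 3 or above, ranges from 0 to 10%.
- Of subjects with baseline 0–2, 6.8% worsen to 3 or above. The figure is borrowed from the combined neurological morbidity and mortality (13/191) of the earlier post-market registry in Protocol 1.2.3.
- Of subjects with baseline 3 or above, 50% are unchanged, 25% improve but stay at 3 or above, 20% improve to 0–2 and 5% worsen.

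Failures are 200(1 − q) × 0.068 plus 200q times:

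- 0.25 + 0.05 = 0.30 (protocol)
- 0.50 + 0.25 + 0.05 = 0.80 (SAP)
- 0.05 (proposed)

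At q = 5% the first term is 190 × 0.068 = 12.92. Adding 10 × 0.30, 10 × 0.80 and 10 × 0.05 gives 15.92, 20.92 and 13.42 failures.

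| q | Protocol | SAP | Proposed |
|---|---|---|---|
| 0% | 6.8% | 6.8% | 6.8% |
| 2% | 7.3% | 8.3% | 6.8% |
| 5% | 8.0% | 10.5% | 6.7% |
| 10% | 9.1% | 14.1% | 6.6% |

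The borrowed 6.8% cancels from the gaps. Protocol minus proposed is 0.25q, and SAP minus proposed is (0.50 + 0.25)q = 0.75q. At most, the SAP gap is q itself, reached if every such subject is unchanged or improves without reaching 2. The protocol gap cannot exceed the share who enter at mRS 4 or 5.

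**The case against.** The case against acting is substantial.

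- **mRS decides nothing.** It is not among the primary or secondary endpoints in SAP section 5 or 7.9, and Protocol 9.2 sets no formal success criteria. Post-treatment harm is captured elsewhere, by major stroke, neurological death and events adjudicated by the clinical events committee. This stands and limits the weight of the point.
- **Baseline is not ignored altogether.** SAP 7.13.3 plans change from baseline, and 7.6 plans a listing of mRS before and after the procedure, so a stable or improved subject can be found. This stands in part: a listing does not correct the reported percentage.
- **Few subjects may be affected.** Hunt and Hess grade up to 3 does not imply mRS 4 or 5. Other exclusions, such as recent clinical worsening at the investigator's judgment, may remove many disabled subjects. This stands; the number could be near zero.
- **No change may have been meant as no worsening.** Perhaps, but neither document says so, and the SAP's formula points the other way.

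A reader might infer three stronger things, none of which the documents support:

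- That neither rule measures harm. Both flag every worsening to mRS 3 or above, and death.
- That the SAP has replaced the composite. Section 7.12 defers to the protocol, and the additional safety and effectiveness analyses in SAP section 5 are redacted, so the composite cannot be called absent.
- That the good-outcome rate is understated by 5 to 10 points. That is only the upper bound under the SAP split when 5 to 10% of subjects are assumed to enter above mRS 2.

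**Conclusion.** The point holds as a defect of definition. On its literal reading, the protocol composite puts three kinds of improver below unchanged subjects with the same baseline. The visible SAP split fails those improvers and unchanged subjects at 3 to 5, differs from the protocol measure and drops last follow-up.

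Under the illustrative transitions, failure is overstated by about 0.25q under the protocol rule and 0.75q under the SAP split. That is 1.25 and 3.75 points at q = 5%, and zero if nobody enters at mRS 3 or above. Both q and the transitions are assumptions. This is a descriptive, non-primary measure; the change is worth making because it is cheap and removes a conflict between the documents.

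**What to change.** 1. In Protocol 3.1 and 9.4 and SAP 7.7 and 7.13.3, define good functional outcome as mRS 0–2 or no worse than baseline, at 1 year and at last follow-up.
2. Keep the split at 2 as a supporting row, labelled as functional status regardless of baseline.
3. Add a shift table of baseline by 1-year mRS. It also shows worsening within 0–2, which all the rules miss.
4. State how a missing baseline is handled. Only subjects with follow-up mRS above 2 need one, since 0–2 is a good outcome whatever the baseline. One option is to count those with follow-up above 2 and no baseline as not having a good outcome, and report their number. Say also whether the mRS required at the procedure serves as baseline when it was recorded before treatment; SAP 7.2.2 takes baseline as the value immediately before the procedure.

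The cost is a wording change in four sections, one table and one missing-data sentence. No new data are collected. The downside is reliance on a baseline score that the SAP schedule makes optional.
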